Assuming a non-inferiority trial with one-sided distribution (face to face training versus computer based training), and power of 90% the sample size is 375 observations (observation=1 video scored). This falls to 271 observations if 0.80 1-beta error is set. As we will use 60 videos per participants, we would need a minimum of 7 participants in each centre. To minimise any potential errors we aim to recruit 10-20 participants from each group (as described above) from each centre.

Objectives

To assess the impact of didactic face-to-face training vs. self-directed computer based training module.

To evaluate the impact of an educational training module has on the ability of clinicians to differentiate small/diminutive polyps.

Outcome Measures

A pre-training assessment will be completed by participants. Performance at predicting histology (neoplastic vs. non-neoplastic) will be assessed using sensitivity, specificity, PPV, NPV and accuracy. The proportion of high and low confidence diagnoses will be also documented.

Following training, participants will immediately complete a post-training assessment and performances will be observed comparing with pre-training assessment. A follow up assessment at 6 months will be completed to assess the retention and sustainability of skills acquired.

Kappa inter-observer variability between the raters will be assessed.

Intervention

Training module: didactic face-to-face classroom training or computer-based self-learning training module

Trial Schema

[figure not shown]

Table of Contents

Protocol development and sign off	2
Key Protocol Contributors	2
[name]	2
[name]	2
[name].....	2
Protocol Amendments	2
CI Signature Page.....	3
Sponsor statement:.....	3
Administrative Information	5
Trial Summar	7
Title	7
Diminutive polyp training module using novel endoscopic imagin: a comparison between didactic training and self-directed computer based training	7
Trial Design	7
Objectives	7
Participant Population and Sample Size	Error! Bookmark not defined.
Outcome Measures	8
Intervention	Error! Bookmark not defined.
Trial Schema	10
Table of Contents.....	11
1. Background and Rationale.....	13
1.1. Trial Rationale	16
1.2. Justification for participant population.....	16
1.3. Justification for design	17
2. Aims, Objectives and Outcome Measures.....	17
2.1. Aims and Objectives	17
2.2. Outcome Measures.....	17
3. Trial Design and Setting	17
3.1. Trial Design.....	17
3.2. Trial Setting	17
4. Eligibility	17

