More recently Rastogi's group sought to identify which training method was more effective in prediction of diminutive polyp histology amongst trainees: didactic face to face training versus computer-based self-learning ²⁶. The participants were randomised to either receive didactic training in the form of a classroom training session or self-learning via computer-based material on characterisation of polyps using NBI. Trainees reviewed 40 videos of diminutive polyps with the histology being revealed and explained. Both groups were given a further 40 videos for testing. This study found those taught in the didactic group characterised polyps with higher confidence, but the overall performance was similar in the two groups. The accuracy and sensitivity were slightly better in the self-learning group (93.9% vs 85.7% p 0.01 and 95.0% vs 86.9%; p0.03 respectively) in those polyps assessed with high confidence. This study demonstrates that a computer-based training module can be as effective in didactic training, perhaps a reflection on the amount of online self-learning trainees are exposed to.

We aim to recruit participants to receive either didactic face-to-face training or self-directed computer based learning, whereby participants will be taught how to characterise lesions using the NICE, BASIC and SIMPLE classification. We aim to recruit trainees, novice endoscopists and experienced endoscopists to compare the different groups. Pre- and post-training assessments will be completed allowing us to examine the impact of training, which will consist of 40-60 videos (equal proportion of NBI, iScan OE and BLI) in the pre-training assessment and 40-60 videos (different set of videos but also equal proportion of NBI, iScan OE and BLI) in the post-training assessment. A follow up assessment will be completed at 6 months to assess the retention of skills and sustainability of colonic polyp characterisation using the optical diagnosis techniques. An existing library of NBI and OE-iScan videos will be used and further videos will be collected during routine colonoscopies with patients consenting for images to be used for teaching purposes.

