5.3. Randomisation

Participants will be randomised into either didactic face-to-face training or computer self-training module. This will take place prior to the training event and participants will be informed of which group they have been allocated on the day by using a computerized stratified randomisation sequence where a computer-generated random number will be assigned to each participant and then randomized to each arm to ensure a balanced number in both groups.

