9.1.4. Power Calculations

Assuming a non-inferiority trial with one-sided distribution (face-to-face training versus computer based training), and power of 90% the sample size is 375 observations (observation=1 video scored). This falls to 271 observations if 0.80 1-beta error is set. As we will use 60 videos per participants, we would need a minimum of 7 participants in each centre. To minimise any potential errors we aim to recruit 14 participants from each centre (7 randomised to face-to-face training and 7 to the computer group).

10. Trial Organisational Structure

There is no trial steering committee needed for this teaching project, The members involved are outlined in the administrative information at the start of this protocol.

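### The sample size treats every scored video as independent although participants are randomised, so the stated 90% power from 375 scores, and the minimum of seven participants per centre derived from it, ignore within-reader correlation

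*Combined protocol and SAP*

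**What the plan says.** Section 9.1.4 sets up the calculation as "Assuming a non-inferiority trial with one-sided distribution (face-to-face training versus computer based training", gives "power of 90% the sample size is 375 observations (observation=1 video scored", and adds "This falls to 271 observations if 0.80 1-beta error is set". It then turns scores into people: "As we will use 60 videos per participants, we would need a minimum of 7 participants in each centre". As protection against error, "we aim to recruit 14 participants from each centre (7 randomised to face-to-face training and 7 to the computer group". The summary repeats the 375, the 271 and the seven, but states a different target: 10-20 participants from each experience group at each centre.

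Section 5.3 fixes the unit of randomisation: "Participants will be randomised into either didactic face-to-face training or computer self-training module". Section 4.1 admits independent colonoscopists with more than 1000 procedures, nurse endoscopists, trainees, and junior doctors or students with no colonoscopy experience. Section 9.1 names Fisher's exact test for the comparison of the groups. No ICC, design effect or between-reader variance appears anywhere. Nor do a non-inferiority margin, an expected accuracy, an alpha for the sample size, or whether 375 is per arm or in total.

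**The concern.** Dividing 375 by 60 is valid only if 60 scores from one reader carry as much information as 60 scores from 60 different readers. Readers with such different experience will differ in accuracy, so scores from the same reader will be correlated. The comparison of arms is then limited mainly by the number of readers, and extra videos per reader add little.

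The figures of 90% and 80% therefore belong to a trial that randomises single videos. A centre, or a trial that stopped near the stated minimum, could report 90% power without having it. Sections 1.1 and 2.1 hypothesise no difference between the two methods, so an inconclusive result from too few readers could be misread as confirming that hypothesis.

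**Working it through.** **1. Reproducing the plan's figures.** The 375 cannot be rebuilt, because the margin, expected accuracy and alpha are not given. Two internal checks are possible.

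- Ratio of the two sizes: 375/271 = 1.384. At one-sided alpha 0.05, (1.645 + 1.282)² / (1.645 + 0.842)² = 1.385, which predicts 271 from 375. At one-sided 0.025 the ratio is 1.339, which predicts 280. The plan therefore appears to use one-sided 0.05; this is inferred, not stated.
- Participants: 375/60 = 6.25, rounded up to 7. This reproduces the minimum exactly, with a design effect of 1.

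**2. Design effect.** With m = 60 videos per reader, DEFF = 1 + (m − 1) × ICC = 1 + 59 × ICC. The ICC values are assumptions.

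| ICC | DEFF | 375 scores are worth | Readers carrying 375 independent scores (375 × DEFF / 60) |
|---|---|---|---|
| 0.02 | 2.18 | 172 | 14 |
| 0.05 | 3.95 | 95 | 25 |
| 0.10 | 6.90 | 54 | 44 |

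For scale, at an assumed accuracy of 85%, ICC 0.05 is a between-reader standard deviation of √(0.05 × 0.85 × 0.15) = 0.08, or 8 percentage points. ICC 0.02 is about 5 points.

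**3. Power without the missing margin.** The plan's own 90% fixes the standardised effect at 1.645 + 1.282 = 2.926 (from unrounded values) for 375 independent scores. For a one-sided t test on participant-level accuracy, the noncentrality is

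2.926 × √(N/375) / √DEFF,

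where N is the number of scores counted on the same basis as 375 (total or per arm). For a 3 v 4 split it is multiplied by √(48/49). Degrees of freedom are readers minus 2.

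Worked at ICC 0.05 (√3.95 = 1.987):

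- Seven readers, 375 as a total: 2.926 × √(420/375) × √(48/49) / 1.987 = 1.54 on 5 df, power 38%.
- 7 v 7, 375 per arm: 2.926 × √(420/375) / 1.987 = 1.56 on 12 df, power 43%.
- 7 v 7, 375 as a total: 2.926 × √(840/375) / 1.987 = 2.20 on 12 df, power 67%.

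| Readers | Basis of 375 | ICC 0.02 | ICC 0.05 | ICC 0.10 |
|---|---|---|---|---|
| 7 (3 v 4) | total | 56% | 38% | 26% |
| 14 (7 v 7), one centre | per arm | 63% | 43% | 30% |
| 14 (7 v 7), one centre | total | 87% | 67% | 47% |

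At ICC 0 the first row gives 83.5%, not 90%, so part of that row's loss comes from the 5-df test and the uneven split. The third row reaches 90% only at an ICC of about 0.015 or less.

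**4. The pooled trial.** The number of centres is not fixed. Five is assumed here, one for each country named in section 3.2.

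| Readers | Basis of 375 | ICC 0.05 | ICC 0.10 |
|---|---|---|---|
| 35 (7 × 5) | per arm | 78% | 57% |
| 35 (7 × 5) | total | 96% | 83% |
| 70 (14 × 5) | per arm | 96% | 83% |
| 70 (14 × 5) | total | above 99% | 98% |

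The summary's target is larger. Ten in each of three experience groups at five centres is 10 × 3 × 5 = 150 readers, which gives over 98% at ICC 0.10 on either basis.

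**The case against.** The strongest reply is that nobody plans a trial of seven readers. Seven is a per-centre figure, section 9.1.4 itself aims for 14 per centre, the summary aims for more, and no centre is to be analysed alone. The 3 v 4 split is a device of this check and is not in the plan. A reader might infer that the whole trial has about 40% power, or that seven per centre is shown to be too few for the pooled comparison. The documents support neither. On the pooled reading, seven per centre over five centres reaches 96% at ICC 0.05 if 375 is a total, and 14 per centre reaches at least 96% at that ICC on both bases. The opposite inference, that no extra recruitment could be needed, is not established either: 70 readers give 83% at ICC 0.10 if 375 is per arm.

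It is also fair that every ICC here is assumed. Section 5.3 calls the randomisation stratified without naming factors, and section 6.2 collects a pre-training score. Adjusting for experience or for that score would lower the residual ICC, though no such adjustment is planned. If all readers score a common video set, video effects partly cancel between arms; the simple design effect covers reader clustering only. And 375/60 is correct as arithmetic. The fault is the independence assumption behind it.

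These points limit the scope. They do not rescue the statement that 375 scores give 90% power, and the plan never says that its calculation is a pooled one.

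**Conclusion.** The concern holds for the stated power and for the stated per-centre minimum. Scores from about seven readers do not give 90% power at any material ICC. At ICC 0.02 to 0.10, some 14 to 44 readers, not seven, carry the information of 375 independent scores. A single centre at the 7 v 7 target has between 30% and 87% power over that range, depending on the ICC and on whether 375 is per arm or a total.

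It does not follow that the pooled trial is underpowered. With the planned recruitment over five centres it may well be adequate; that depends on the ICC, the basis of 375 and which recruitment target applies. The figures rest on assumed ICCs, one-sided alpha 0.05 inferred from 375:271, 60 videos per reader, and a participant-level t test. The Background allows 40-60 videos per assessment, so m also needs to be fixed.

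**What to change.** In section 9.1.4 and the summary:

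- Replace the observation-based statement with participants per arm over the whole trial, pooled across centres, using DEFF = 1 + (m − 1) × ICC. State the assumed ICC and a range, for example 0.05 with 0.02 to 0.10. The pre-training assessment, completed before the training day, can be used to check it.
- State the non-inferiority margin, the expected accuracy, alpha, and whether 375 is per arm or a total. Without these the calculation cannot be redone.
- Reconcile 14 per centre with 10-20 per experience group per centre, and restate the power that the planned recruitment gives.
- Remove the claim that seven participants per centre give 90% power.

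In section 9.1, so that the analysis matches the restated power, compare arms on participant-level accuracy or with a model that includes a participant effect, such as a mixed logistic model. Fisher's exact test on pooled video scores would understate the standard error by a factor of about √3.95 = 2 at ICC 0.05, even where the pooled number of readers is ample.

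The cost is rewording and a short recalculation. The downside is a less favourable stated power for a single centre. Whether the pooled recruitment reaches 90% has to come out of the recalculation.

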10.1. Sponsor

University of Birmingham will be the sponsor for this teaching project.

This project will be run and conducted by the Institute of Translational Medicine

11. Confidentiality and Data Protection

Consent for the holding of participant data and publication of findings will be gained from participants online prior to starting the pre and post training assessments.

12. Insurance and Indemnity

The University of Birmingham has in place Clinical Trials indemnity coverage for this trial which provides cover to the University for harm which comes about through the University's, or its staff's, negligence in relation to the design or management of the trial and may alternatively, and at the University's discretion provide cover for non-negligent harm to participants.

13. Access to the final trial dataset

[name], [name] and [name] will have access to the full data set throughout this study

14. Publication Policy

It is intended that the results of the study will be reported and disseminated at international conferences such as the British Society of Gastroenterology annual meeting, the United European Gastroenterology Week (UEGW) and the Digestive Diseases Week (DDW) and in peer-reviewed scientific journals such as *Endoscopy*, *Gastrointestinal Endoscopy* and *Gut*. Results will also be disseminated to the local primary care groups, the Oxford and Wessex 'Gut Club' and also to patients via the endoscopy staff and patient forum.

15. Reference List

References:

Appendix 1.

NICE classification:

Type 1: Hyperplastic

Colour: same or lighter than background

Vessels: none, or isolated lacy vessels coursing across the lesion

Surface pattern: dark or white spots of uniform size, or homogenous absence of pattern.

Type 2: Adenoma

Colour: browner relative to background (verify colour comes from vessels)

Vessels: brown vessels surrounding white structures

Surface pattern: oval, tubular or branched white structures surrounded by brown vessels.

Type 3: deep submucosal invasive cancer

Colour: brown to dark brown relative to background; sometimes patchy white areas

Vessels: Has area (s) of disrupted or missing vessels

Surface pattern: Amorphous or absent surface pattern

The SIMPLE (Simplified Identification Method for Polyp Labelling during the Endoscopy) classification (Iacucci M et al Endoscopy in press) was recently developed with the addition of criteria for Sessile Serrated Adenoma (SSA):

Type 1: Hyperplastic

Surface pattern: Round pit

Vessels: None, isolated lacy

Lesion border: Regular

Type 2a: Sessile serrated adenoma/lesion

Surface pattern: Open/dilated (dark) pit

Vessels: None, isolated lacy

Lesion border: Irregular/indistinctive

Type 2b: Adenoma

Surface pattern: Not round structure: oval, tubular, branched

Vessels: Thick vessels

Lesion border: Regular
